# 13 Quality Assurance and Control

## 13.1 Data Management

Data management processes for handling study data will be maintained by the Sponsor.

UAB Ligence	Clinical Investigation Report	2021-04-09
		Rev: 1.0

## 13.2 Completion of Case Report Forms (CRFs)

The data reported on the CRFs shall be derived from source documents and be consistent with these source documents. Electronic form of CRFs will be used. The Sponsor will provide CRFs and train study staff on completion of CRFs during the training on clinical investigation plan.

CRFs are considered to be the reports generated while using Ligence Heart software. CRFs are completed using the software. CRFs certified by signing in and approving the report with the accounts individually assigned to each investigator. The Principal Investigator is ultimately responsible for ensuring completion of CRFs.

If discrepancies are discovered on paper CRFs during monitoring, the Sponsor's CMO will ensure that the study staff makes necessary corrections directly to the CRF(s) prior to collection.

If a site discovers discrepancies after CRF collection, the site may notify the Sponsor and request data modification.

## 13.3 Data Handling and Record Keeping

All documents and data shall be produced and maintained in a manner that assures control and traceability.

## 13.4 Source Data and Documents

Source data includes information in original records, certified copies of original records of clinical findings, observations, or other activities for the study. Source documents for each subject must be retained throughout the investigation, including printed or electronic documents containing source data.

The Principal Investigator or institution shall provide direct access to source data during and after the clinical investigation for monitoring, audits, EC review, and regulatory authority inspections.

## 13.5 Archiving

All study data must be archived for a minimum of 3 years after study termination (or as required by local law) or premature termination of the clinical investigation. No source documents or study records will be destroyed without Sponsor notification and approval.

# 14 Monitoring Plan

In collaboration with the site, the Sponsor will ensure proper monitoring of the study to confirm that all the research requirements are met. The Sponsor will oversee the progress of a clinical investigation and ensure that it is conducted, recorded, and reported in accordance with the protocol, written procedures, Good Clinical Practice (GCP) ISO 14155:2011, and the applicable regulatory requirements.

## 14.1 Confidentiality and Data Protection

The investigator affirms and upholds the principle of the subject's right to privacy, and the investigator shall comply with applicable privacy laws. Especially, anonymity of the participants shall be guaranteed when presenting the data at scientific meetings or publishing data in scientific journals.

Individual subject medical information obtained as a result of this study will be considered confidential, and disclosure to third parties will be prohibited. Subject confidentiality will be further ensured by utilizing subject identification code numbers, that is, all data provided to the Sponsor will be pseudonymized and will not contain any personal information. For data verification purposes a competent authority (CA), or an

UAB Ligence	Clinical Investigation Report	2021-04-09
		Rev: 1.0

ethics committee (EC) may require direct access to parts of the medical records relevant to the study, including subject medical history.

## 14.2 Storage of Images and Associated Health Data

Research images and associated data will be collected and disclosed to the Sponsor as part of this study. Fully de-identified data, which has had all personal identifying information removed, may be stored and used by the Sponsor indefinitely. The Sponsor and/or its authorized representatives may use any de-identified data collected in this study for future technology and engineering development, marketing purposes, education, regulatory claims, or other possible uses.

## 14.3 Publication Policy

The results of this study may be used in future publications, at the discretion of the Sponsor. The conditions of publication are described in a separate contractual agreement. The investigator should in good faith make the Sponsor aware of any possible public scientific contributions, such as publications or presentations. The Sponsor may request modifications or to delay presentations at its discretion.

# 15 Investigation Results

## 15.1 Demographic data

A total of 58 persons from a single center in Lithuania referred to 2D transthoracic echocardiography (TTE) in non-emergency setting were enrolled in the study retrospectively. Among the participants, 100% were Caucasian, 50.0% were female. The mean LVEF was  $50.81 \pm 9.77\%$ , with 13.79% of the participants having LVEF < 50%. The median age was 62.0 years. All participants had sinus rhythm at the time of performing TTE (Table 1a and 1b).

**Table 1a.** Main parameters of the study cohort.

	Mean	± SD
Age (years)	62.05	14.92
Weight (kg)	83.17	14.25
Height (cm)	172.57	10.36
Body surface area	1.99	0.21
Ejection Fraction (%)	50.81	9.85

**Table 1b.** Main descriptive statistics.

	N	(%)
Females	29	50.00
History of Heart Failure	29	50.00
History of Myocardial Infarction	11	18.97
History of Percutaneous Coronary Intervention	14	24.14
History of Coronary Artery Bypass Graft	4	6.90

UAB Ligence	Clinical Investigation Report	2021-04-09
		Rev: 1.0

History of Arterial Hypertension	1	1.72
History of Valvular Heart Disease	43	74.14
History of Coronary Heart Disease	14	24.14
History of Cardiomyopathy	3	5.17
Implantable Device (Pacemaker or Defibrillator)	3	5.17

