Transposition of the great arteries (except for patients with arterial switch operation)

UAB Ligence	Clinical Investigation Report	2021-04-09
		Rev: 1.0

Univentricular heart (including double inlet left/right ventricle, tricuspid/mitral atresia, hypoplastic left heart syndrome, any other anatomic abnormality with a functionally single ventricle)
Truncus arteriosus
Other complex abnormalities of atrioventricular and ventriculoarterial connection (i.e. crisscross heart, heterotaxy syndromes, ventricular inversion).
Congenital tricuspid and pulmonary valve disease
Situs inversus or dextrocardia
Heart tumors
Prosthetic valves, post-operative heart valves, cardiac geometry changing cardiothoracic surgeries
Implanted dual-chamber or ventricular pacemaker
Bi-ventricular resynchronizator
cardioverter-defibrillator
Left ventricle assisting device, Right ventricle assisting device

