#### 6.5.2 Exclusion Criteria

UAB Ligence	Clinical Investigation Report	2021-04-09
		Rev: 1.0

Subjects will be excluded that:

- Have anatomical or functional cardiac characteristics that prevent appropriate completion of 2D TTE image analysis using the study device - a list of such characteristics can be found in the section 4.6.2 Contraindications;

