## 8.2 Exploratory Assessments

The Principal Investigator collects descriptive statistics data from the enrolled subjects that have been enrolled before they are sent to the IT staff for pseudonymization. The following descriptive statistics data will be collected:

- Gender
- Age (years)
- Weight (kg)
- Height (cm)
- Ethnicity
- Ultrasound machine model
- Total number of DICOM files
- History of heart failure
- History of myocardial infarction
- History of percutaneous coronary intervention (PCI)
- History of open cardiac surgery
- Atrial fibrillation
- History of arterial hypertension
- History of valvular heart disease
- History of congenital heart disease
- History of cardiomyopathy
- History of implanted devices/closures/prostheses

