## 15.2 Accuracy of automatic measurements (Part 2)

In order to establish the baseline inter- and intra-observer variability, the original rater group (ORG) consisting of three board certified cardiologists analyzed 58 2D TTE studies, repeating the measurements twice. This generated six values for each measurement in each study. The new rater group (NRG) consisting of a fourth cardiologist (FC) and Ligence Heart performed measurements in the same 58 studies. NRG performance was evaluated by calculating the number of measurements of each type that were in the limits of variation. FC was used as the performance benchmark for Ligence Heart.

There was no significant difference in variation between Ligence Heart and FC ( $p > 0.05$ ) and Ligence Heart had non-inferior accuracy to FC for all automatic measurements (**Table 3**). The lowest number of studies in agreement with ORG was 93.1% in RAA and 94.55% in RVM for Ligence Heart and FC, respectively. For AoS, STJ, IVSd, LVEDD, LVESD, LVESV4A and RVOTPD both FC and Ligence Heart were in agreement with ORG for 100% of studies. Ligence Heart discarded 2-4 studies in RAMAD, LAV4A, LVEDV4A, LVESV4A, LVEDV2A, LVESV2A, RVEDA and RVESA due to insufficient quality scores of automatic predictions (**Table 3**). Ligence Heart confidence interval for the number of studies in agreement with ORG intersected FC for all automatic measurements (**Figure 1**) and comparing each measurement between FC and Ligence Heart yielded a median Pearson correlation R 0.74 (IQR 0.59-0.83) (**Figure 2**).

Comparison of correlation between all raters and NRG measurement relation to ORG measurements is visualized in **Supplementary figures 1 and 2**, respectively.

**Table 3.** Comparison of Ligence Heart and cardiologist agreement with original rater group.

Measurement	Ligence Heart studies in agreement with ORG (95% CI)	FC studies in agreement with ORG (95% CI)	P-value*	N studies	N studies not passing confidence filter in Ligence Heart	Pass
RAMAD	96.3 ± 5.03	98.15 ± 3.59	0.56	54	4	Yes
AoA	98.28 ± 3.35	98.28 ± 3.35	1	58	0	Yes
AoS	100.0 ± 0.0	100.0 ± 0.0		58	0	Yes
STJ	100.0 ± 0.0	100.0 ± 0.0		58	0	Yes
AAo	98.28 ± 3.35	100.0 ± 0.0	0.32	58	0	Yes
LAD	94.83 ± 5.7	100.0 ± 0.0	0.08	58	0	Yes
LAV4A	98.21 ± 3.47	94.64 ± 5.9	0.31	56	2	Yes
IVSd	100.0 ± 0.0	100.0 ± 0.0		58	0	Yes
LVPWd	96.55 ± 4.7	100.0 ± 0.0	0.16	58	0	Yes
LVEDD	100.0 ± 0.0	100.0 ± 0.0		58	0	Yes
LVESD	100.0 ± 0.0	100.0 ± 0.0		58	0	Yes
LVEDV4A	98.21 ± 3.47	100.0 ± 0.0	0.32	56	2	Yes

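### Table 1b counts three subjects with a pacemaker or defibrillator although section 6.5.2 excludes most such devices, and Part 2 reports neither a deviation nor an analysis without them

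*Protocol*

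**What the plan says.** Section 6.5.2 excludes subjects who "Have anatomical or functional cardiac characteristics that prevent appropriate completion of 2D TTE image analysis using the study device" and refers to section 4.6.2 for the list. Among the entries of that list are "Implanted dual-chamber or ventricular pacemaker" and "cardioverter-defibrillator", as well as biventricular resynchronisation devices. Under section 6.6, step 4, the principal investigator assesses each randomly drawn study against the criteria and asks for another if it is unsuitable.

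The results sections of the same document report: "A total of 58 persons from a single center in Lithuania referred to 2D transthoracic echocardiography (TTE) in non-emergency setting were enrolled". Table 1b gives 3 of these 58 (5.17%) in its row "Implantable Device (Pacemaker or Defibrillator", without the device type. Section 15.2 says that the fourth cardiologist and the software "performed measurements in the same 58 studies" as the original three raters. Sections 15 and 16 mention no protocol deviation, no explanation and no analysis without these subjects. The limitations in section 16.4 name sinus rhythm, the single centre and the two ultrasound manufacturers, but not this.

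**The concern.** The eligibility rule and the description of the analysed cohort do not fit together. Section 4.6.2 says that the automatic functions should not be used on images from patients with the listed conditions. Section 16.2 then concludes non-inferiority of those functions from a cohort that appears to include such patients.

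Two features of Part 2 make three subjects matter:

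- Agreement in Table 3 is close to 100% for both raters, so the comparison turns on a handful of studies.
- Under sections 12.5.1 and 12.5.2, the SEM and MDC come from an ANOVA over all patients measured by the first three cardiologists. If device images vary more between raters than the rest, they widen the limits applied to every study. If they vary less, they narrow them. The document does not show which.

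**Working it through.** **Step 1: the passages side by side.**

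| Place | Content |
|---|---|
| 4.6.2 | Lists dual-chamber or ventricular pacemakers, resynchronisation devices and cardioverter-defibrillators |
| 6.5.2 | Excludes subjects with listed conditions |
| 6.6, step 4 | Unsuitable studies are replaced by new random ones |
| Table 1b | 3 subjects with pacemaker or defibrillator; 3/58 = 5.17%, as printed |
| 15.2 | Part 2 starts from all 58 studies |

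Defibrillators are listed without qualification. For pacemakers the list names two types, so a pacemaker of another type would be off the list. If the row label is right, all three subjects can be eligible only if each has such an unlisted device, or had no device when the examination was made.

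**Step 2: reproduce the stated minimum of 54.** Inputs from section 12.2: f = 0.25, α = 0.05, power 0.95, k = 3 groups, m = 2 measurements, ρ = 0.6. For the within-between interaction, λ = f²·N·m/(1 − ρ) = 0.0625 × N × 2/0.4 = 0.3125·N, with df1 = (k − 1)(m − 1) = 2 and df2 = (N − k)(m − 1) = N − 3. The smallest N with power of at least 0.95 is 53 (0.952). Rounded up to three equal groups it is 54 (λ = 16.875, df2 = 51, power 0.956). The plan's figure is reproduced.

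**Step 3: remove the three subjects.** Overall, 58 − 3 = 55, one above the minimum, with power 0.959. Per measurement in Table 3, the result depends on how many of the three the confidence filter had already dropped, which the document does not say:

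| N in Table 3 | Measurements | N without the three | Power at the lowest N |
|---|---|---|---|
| 58 | 10 measurements | 55 | 0.959 |
| 56 | LAV4A, LVEDV4A, LVESV4A | 53 to 55 | 0.952 |
| 55 | RVB, RVM, RVEDA, RVESA | 52 to 55 | 0.948 |
| 54 | RAMAD, LVEDV2A, LVESV2A, RAA | 51 to 54 | 0.943 |

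**Step 4: compare with the differences in Table 3.** Turning percentages into counts (for example LAD: 94.83% of 58 = 55, so 3 outside the limits against 0), 12 of the 21 measurements show a non-zero difference between the software and the fourth cardiologist:

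- 1 study: RAMAD, AAo, LVEDV4A, RVEDA, RVESA
- 2 studies: LAV4A, LVPWd, LVEDV2A, LVESV2A, RAA
- 3 studies: LAD, RVM

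Three subjects therefore equal the largest difference in the table.

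**Step 5: could a Pass entry change?** With the limits held fixed, deleting three subjects can produce nothing more extreme than 3 against 0 studies outside the limits. LAD already shows that pattern, with p = 0.08 at N = 58, and a two-sample t-test still gives p = 0.08 at N = 51. No Pass entry would change. With recomputed SEM and MDC limits, the document gives no data from which to tell.

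**The case against.** The strongest reply is that ineligibility is not proven. Section 4.6.2 does not list every pacemaker, and Table 1b gives no device type. The examinations span ten years, and under section 6.6, step 5, clinical data were taken from the files after inclusion, so the row may not show device status at the examination. The principal investigator also screened every study. All of this stands. It is why the first step is a source check, but it does not remove a contradiction that the document leaves unexplained.

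It is also fair that no effect on the results is shown, and that redefining the primary set after the results are known would be a post hoc change. Showing both sets side by side meets that objection.

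A reader might infer two stronger points that the documents do not support:

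- **The analysis set falls below 54 without these subjects.** It does not, since 55 remain. A shortfall is possible only for single filtered measurements. Moreover, 54 was derived for a repeated-measures ANOVA interaction, whereas section 16.2 describes a t-test for the Table 3 comparison. The threshold therefore says little about the power of that comparison.
- **Subjects with congenital disease were also enrolled.** Section 8.2 lists "History of congenital heart disease" and atrial fibrillation. Table 1b has neither, shows coronary heart disease instead, and prints hypertension 1 beside valvular disease 43. This could suggest rows shifted by one. It is speculation, and such a shift would move the last 3 to cardiomyopathy and leave no device count at all. The oddity supports a check of the labels and nothing further.

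**Conclusion.** The point holds as an internal contradiction. As printed, Table 1b places 3 of 58 subjects (5.17%) in a category that sections 4.6.2 and 6.5.2 largely exclude, and Part 2 was reported without a deviation or an analysis that leaves them out. A breach is likely but not proven. It rests on the row label being right, on at least one of the three having a listed device type, and on that device being present at the examination.

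The weight comes from the small margins in Table 3 (1 to 3 studies) and from the subjects' part in setting the SEM and MDC limits. The direction of any effect is unknown. The sample-size consequence is minor: in the worst case, four measurements fall to 51 studies, where power by the section 12.2 calculation is 0.943, less than one percentage point under the planned 0.95.

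**What to change.** 1. Check against source, for the three subjects, the device type and whether the device was present at the examination. Check the row labels of Table 1b against the variable list in section 8.2.
2. Reconcile sections 4.6.2, 6.5.2 and Table 1b, and state the device types in the table or a footnote.
3. If any subject is confirmed ineligible, report the deviation under section 11.3. Recompute the ANOVA, the SEM and MDC limits and all of Table 3 in the protocol-eligible subjects, and show these results beside those for all 58. Deleting three rows under the old limits is not enough. State for each measurement how many of these subjects the confidence filter had already dropped.

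The cost is one source check and, if needed, one re-run of the Part 2 tables, with N lower by at most 3. No new measurements are required.

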## 15.1 Manual functionalities (Part 1)

All measurements performed manually using Ligence Heart were equally accurate and reliable when compared to state-of-the-art certified medical image analysis software. Median inter-software reliability was 95.52% (IQR 94.31 - 97.17) with the lowest value observed for RAA (89.30%) and the highest for APV (99.26%). All tested measurements had inter-software reliability above 0.8, corresponding to high level of agreement between different platforms (**Table 2**) and there was no significant difference in the measurements produced by Ligence Heart in comparison to other CE marked state of the art medical device software.

**Table 2.** Inter-software reliability for Ligence Heart compared to EchoPAC and Intellispace Cardiovascular.

Measurement (abb.)	Measurement (full)	Inter-software reliability
AoS	Aortic sinus diameter	97.81%
RVB	Right ventricle basal diameter	93.28%
LVEDV4A	Left ventricle end diastolic volume (A4Ch)	97.12%
LVEDV2A	Left ventricle end diastolic volume (A2Ch)	93.95%
RVEDA	Right ventricle end diastolic area	92.17%
RAA	Right atrium area	89.30%
APV	Aortic peak velocity	99.26%
PTRV	Peak tricuspid regurgitation velocity	97.18%
E	Transmitral E velocity	99.21%
SP	S prime right ventricle lateral wall	97.16%
Dec	Transmitral E velocity deceleration time	95.41%
ACT	Acceleration time	95.52%
AVVTI	Aortic valve maximum velocity time integral	98.21%
TR VTI	Tricuspid regurgitation velocity time integral	94.66%
LVEDV	Left ventricle end diastolic volume (biplane)	95.52%

UAB Ligence	Clinical Investigation Report	2021-04-09
		Rev: 1.0

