## 7.2 Subject Procedure

### Part 1

The purpose of the procedure in the Part 1 is to calculate the accuracy of Ligence Heart manual functions that are used to perform echocardiographic measurements comparing it with the accuracy of manual measurements performed with other CE marked state-of-the-art medical image viewers. Measurements made in Ligence Heart software will be compared with CE marked software “IntelliSpace Cardiovascular 5.1” (Phillips) and “EchoPAC” version 112 from GE Healthcare.

One cardiologist will perform 2D TTE measurements of each patient on each system 2 times. Time difference between repeated measures must be at least two days.

### Part 2

The purpose of the procedure in the Part 2 is to compare Ligence Heart automatic measurements accuracy and reliability with human cardiologists in real clinical setting.

Four physicians will make 2D TTE measurements of each subject study 2 times. Physicians cannot share thoughts or results between themselves. Time difference between repeated measures must be at least two days. Measurements of three physicians will be used in modeling and results of the 4th will be used as a validation with automated system.

During both parts, time used for the analysis of the 2D TTE images will be recorded. During manual 2D TTE image analysis, time it takes for physician to make measurements will be registered. Stopwatch starts when physician opens study in Ligence Heart and stops when all listed measurements are made. In the use case including automatic measurements, the time it takes for automatic system to make measurements and physician to correct/validate the results is registered.

Summary of the clinical investigation parts

#	Analysis	Purpose	TTE Examination Protocol	Measurements
Part 1	Manual Measurement Analysis	To calculate the accuracy of Ligence Heart manual functions that are used to perform echocardiographic measurements comparing it with the accuracy of manual measurements performed with other CE marked state-of-the-art medical image viewers.	One physician will make 2D TTE measurements of each patient on each system 2 times. Time difference between repeated measures must be at least two days.	
 
• AoS (PLA)
 
• RVB (A4CH)
 
• LVEDV (A4CH)
 
• LVEDV (A2CH)
 
• RVEDA (A4CH)
 
• RAA (A4CH)
 
• AV-Vmax
 

UAB Ligence	Clinical Investigation Report	2021-04-09
		Rev: 1.0

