## 12 Statistical Methods

### 12.1 Statistical Hypotheses

UAB Ligence	Clinical Investigation Report	2021-04-09
		Rev: 1.0

The following hypotheses will be tested with the statistical methods:

1. The manual functionalities of Ligence Heart provide equally accurate tools for echocardiography evaluation compared to other state of the art CE marked medical software.
2. Automatic functionalities of Ligence Heart software perform echocardiography image analysis with non-inferior accuracy compared to a cardiologist.
3. Automatic functionalities of Ligence Heart software perform echocardiography image analysis with lower intra-rater variability compared to a cardiologist.
4. Automatic functionalities produce measurement values faster than a cardiologist.

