## 12.4 Manual Functionalities Analysis (Part 1)

### 12.4.1 Statistical Methods Values and Characteristics

Two-way ANOVA – test used to detect any overall differences between related means.

ANOVA characteristics

Source of variation	Degrees of Freedom	Mean Square
Patient	n - 1	MSS
Software	t - 1	MSR

UAB Ligence	Clinical Investigation Report	2021-04-09
		Rev: 1.0

Error (Patient x Software)	(n - 1)(t - 1)	MSSR
Error (Software)	nt(m - 1)	MSE

ANOVA variance components

Estimates of Variance Components
$\hat{\sigma}_S^2 = \frac{MSS - MSE}{mt}$
$\hat{\sigma}_R^2 = \frac{MSR - MSSR}{mn}$
$\hat{\sigma}_{SR}^2 = \frac{MSSR - MSE}{m}$
$\hat{\sigma}_e^2 = MSE$

Intrater reliability coefficient characterizes reliability of two different raters to measure subjects similarly. Coefficient calculation formulas are given below:

$$\rho = \frac{\hat{\sigma}_S^2}{\hat{\sigma}_S^2 + \hat{\sigma}_R^2 + \hat{\sigma}_{SR}^2 + \hat{\sigma}_e^2}$$

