#### 12.4.2 Data analysis

Two-way ANOVA will be employed to test for significant differences between measurements made in different medical imaging software. Interrater reliability coefficient and Pearson correlation coefficient will be calculated to check the level of interchangeability between software.

Intrater reliability coefficient interpretation

Interpretation	Value
Slight	0.00-0.20
Fair	0.21-0.40
Moderate	0.41-0.60
Substantial	0.61-0.80
Almost perfect	0.81-1.00

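### Part 1 infers equal accuracy from a reliability above 0.8 and a non-significant ANOVA, and neither bounds the error between systems in measurement units

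*Protocol*

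**What the plan says.** Section 12.1 states the Part 1 hypothesis: "The manual functionalities of Ligence Heart provide equally accurate tools for echocardiography evaluation compared to other state of the art CE marked medical software". It gives no margin.

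Section 7.2 sets the design: "One cardiologist will perform 2D TTE measurements of each patient on each system 2 times". There are three systems, the two runs are at least two days apart, and section 8.1 lists 15 measurements.

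Section 12.4.1 defines the coefficient as ρ = σ²_S / (σ²_S + σ²_R + σ²_SR + σ²_e), with components for patient, software, patient-by-software and repeat error.

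Section 12.4.2 plans two things. The first is a difference test: "Two-way ANOVA will be employed to test for significant differences between measurements made in different medical imaging software". The second is a pair of coefficients: "Interrater reliability coefficient and Pearson correlation coefficient will be calculated to check the level of interchangeability between software". It adds verbal bands, the top one being 0.81–1.00, but sets no pass mark and no limit in measurement units.

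Section 15.1 (Manual functionalities) then reports: "All tested measurements had inter-software reliability above 0.8, corresponding to high level of agreement between different platforms". It adds that there was no significant difference and concludes: "All measurements performed manually using Ligence Heart were equally accurate and reliable when compared to state-of-the-art certified medical image analysis software". Section 16.1 goes further: it treats the lack of statistically significant variation as proof that the software can be used for image analysis.

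**The concern.** Accuracy of a measurement tool is a matter of error in mm, cm², mL, cm/s or ms. Neither ground used in section 15.1 is on that scale.

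- **The reliability coefficient is relative.** It compares error with the spread between patients, so the same software error earns a high value in a varied cohort and a low one in a uniform cohort. Its denominator also adds the single reader's repeat error to the software components, so it cannot say how much of the error belongs to the software.
- **The ANOVA does not fill the gap.** The software main effect detects only a shift in the mean. Disagreement that varies from patient to patient does not move that effect. It enlarges the patient-by-software term against which the effect is tested, and so makes significance harder to reach. A non-significant result is not evidence of equality in any case.

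This is a pre-market performance claim. Software whose values scatter around the comparators within a patient could satisfy both grounds and still be described as equally accurate. A reader also cannot tell from Table 2 what error in clinical units to expect.

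**Working it through.** **1. The reported figures.** The 15 values in Table 2 give a median of 95.52%, a minimum of 89.30% (RAA) and a maximum of 99.26% (APV), as stated. The lower quartile reproduces at 94.31. The upper quartile comes out at 97.50 by the same rule, against the stated 97.17; this does not affect the point.

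**2. From ρ to a difference between systems.** Let v be error variance divided by patient variance. The section 12.4.1 formula gives v = (1 − ρ)/ρ. If the error components are random and alike across systems, two single readings of one patient on two systems differ with SD √(2v) in patient-SD units. Under normality the 95% limits are ±1.96·√(2v).

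| ρ | v | SD of difference | 95% limits | Pairs beyond 1 patient SD |
|---|---|---|---|---|
| 0.80 (mark in 15.1) | 0.2500 | 0.707 | ±1.39 | 16% |
| 0.81 (floor of top band) | 0.2346 | 0.685 | ±1.34 | 14% |
| 0.893 (RAA, lowest) | 0.1198 | 0.490 | ±0.96 | 4% |
| 0.9552 (median) | 0.0469 | 0.306 | ±0.60 | 0.1% |
| 0.9926 (APV, highest) | 0.0075 | 0.122 | ±0.24 | about 0% |

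Limits of exactly ±1 patient SD correspond to ρ = 0.885. Every reported value is above that.

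**3. Dependence on patient spread.** Hold the absolute error that gives ρ = 0.81 and multiply the patient SD by k. Then ρ′ = 1/(1 + v/k²).

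- k = 0.5: 1/(1 + 0.2346/0.25) = 0.52, which section 12.4.2 calls moderate.
- k = 1.5: 1/(1 + 0.2346/2.25) = 0.91, which is in the top band.

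**4. Does the ANOVA tighten the mark?** This was simulated with 58 patients, two runs and the Protocol's own variance-component formulas. Assumed, not from the document: repeat variance 0.03 and background patient-by-software variance 0.02 of patient variance, no mean shift, and an extra patient-specific error in one device only. A pass means that ρ rounds to at least 0.81 and that F = MSR/MSSR has p > 0.05. The limits are ±1.96·√(τ² + 2(0.02 + 0.03)), where τ is the extra device error SD.

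| τ (patient SD) | True 95% limits, device vs comparator | Pass, two systems | Pass, three systems |
|---|---|---|---|
| 0.5 | 1.96·√0.35 = ±1.16 | about 88–90% | about 92–94% |
| 0.6 | 1.96·√0.46 = ±1.33 | about 66–69% | about 87–88% |

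The ranges cover repeated runs. The two grounds together usually let such a device through.

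**5. What cannot be computed.** The Protocol gives no patient SDs for the Part 1 measurements, so none of these limits can be put into mm, cm² or mL. Table 2 also gives one coefficient per measurement, so the limits in step 2 are an average over pairs of systems. They do not isolate Ligence Heart against either comparator.

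**The case against.** Several counterarguments have force.

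- **Reliability is the stated objective and endpoint.** Sections 5.2.1 and 5.3.1 ask for inter-software reliability, and the formula is of the absolute-agreement kind: a mean shift between systems lowers it. This stands, and it is why the coefficient should be kept. It does not license the step from reliability to equal accuracy.
- **0.8 is not a prespecified pass mark.** Section 12.4.2 gives interpretation bands only, section 15.1 rests on two grounds, and section 16.1 cites non-significance alone. This stands. The criticism is of the inference from the two grounds together.
- **Repeat error works against the device.** It lowers ρ, and part of the ±1.34 is the reader's own variation. If all the error at ρ = 0.80 were repeat error and the two runs were averaged, the limits would be 1.96·√(2·0.25/2) = ±0.98. This stands, and it is a reason to report the two sources apart.
- **The weakest values may be ordinary repeat error.** Table 4 gives run-to-run correlations for Part 2 cardiologists of 0.88–0.90 for RAA, 0.66–0.75 for RVEDA and 0.74–0.78 for RVB, against Part 1 reliabilities of 0.893, 0.922 and 0.933. The statistics differ and the readers may too, but nothing here points to excess software error.

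A reader might infer that Ligence Heart readings do differ from the comparators by more than one patient SD. The documents do not support that. At the mark, one patient SD is exceeded in about 14–16% of pairs and is not the typical difference; and every reported value implies limits below one patient SD.

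**Conclusion.** The point holds as a criticism of the inference and its wording. A reliability above 0.8 with a non-significant ANOVA does not establish equal accuracy, because together they would still admit 95% limits of about ±1.3 to ±1.4 patient SD. The observed values imply about ±0.96 (RAA) to ±0.24 (APV), with a median of about ±0.60. The study therefore shows high reliability in this cohort. It shows neither large disagreement nor equality in measurement units.

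The limits rest on the section 12.4.1 formula, normality, single readings, and errors alike across systems. The pass rates also rest on the assumed variances in the simulation; the algebra does not need them.

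**What to change.** 1. In section 12.4.2 and Table 2, for each of the 15 measurements, add Ligence Heart minus each comparator as a mean difference and 95% limits of agreement, with confidence intervals, in measurement units.
2. Report software error √(σ²_R + σ²_SR) separately from repeat error √(σ²_e). Both come from the planned ANOVA.
3. Keep ρ as the descriptive reliability endpoint. State that neither ρ above 0.8 nor p > 0.05 is proof of equality.
4. Reword sections 15.1 (Manual functionalities) and 16.1 to report the observed reliability and limits of agreement in place of equal accuracy and proof.
5. Because the document already contains the results, label any acceptance limit added now as post hoc (for example, one tied to the same reader's repeat error), and prespecify it for later studies.

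The cost is some wording and an added table from the existing two-run data, with no new readings. The downside is a weaker Part 1 claim for measurements whose limits prove wide.
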